Renal Disease. Obesity causes and complicates diabetes and hypertension, the two most common causes of kidney failure (Wiggins 2005). Furthermore, obesity in its own right can cause renal disease and may accelerate injury in glomerulonephritides (De Jong 2002). The mechanisms for the adverse effects of obesity on the kidney include its hypertensive and diabetogenic effects. Additionally, adipogenic hormones may have direct injurious actions in the kidney (Coresh 2004). Thus, weight loss is likely to improve indices of renal function. However, bariatric surgery itself has been associated with progressive renal disease through a variety of mechanisms (Khurana 2004). Renal function will be measured by serum creatinine and cystatin and urinary albumin and creatinine (spot urine).

It is hypothesized that albuminuria, the most sensitive index of chronic kidney disease, will diminish after successful bariatric surgery and that the renal function as reflected by serum creatinine will remain stable after successful bariatric surgery (Holzwarth 2002).

Liver Function and Size. The apparent increased prevalence of various forms of non-alcoholic fatty liver disease (NAFLD) in the obese population (Haynes 2004), and the growing identification of NAFLD when sought by liver biopsy among patients undergoing bariatric surgical procedures (Abrams, 2004) have both been the subject of recent publications. The limited data available thus far indicate that it would be important to determine the presence of NAFLD and define the prevalence of advanced forms, such as non-alcoholic steatohepatitis (NASH) and cryptogenic cirrhosis, by systematic intra-operative liver biopsy in a well defined bariatric surgical population. When a liver biopsy is taken during surgery as part of the clinical institution's standard practice, a portion will be studied by LABS investigators. The thickness of the left lobe of the liver will be assessed using a standardized measuring technique.

It is hypothesized that the prevalence and severity of the spectrum of non-alcoholic fatty liver disease are underestimated by traditional laboratory parameters, clinical assessment, and intra-operative visual inspection of the liver (Gholam 2002, Spaulding 2003). Additionally, it is hypothesized that severity of

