Variable	Measurement	Variable(s)	Measurement		
Weight Loss and Body Composition:					
Max. weight loss	Continuous	Gender, diabetes, surgical technique	Categorical	Patient	Analysis of covariance (ANCOVA)
Max. Δ in fat mass	Continuous				
Max. Δ in fat free mass	Continuous	Physical activity level (pre-op and post-op)	Continuous	Patient	Linear regression
Max. Δ in waist circumference	Continuous				
Max. Δ in neck circumference	Continuous				
Patterns of weight loss	Continuous	SAME AS ABOVE	SAME AS ABOVE	Visit	Linear mixed models, piece-wise linear mixed models, non-linear hierarchical models
Pattern of weight regain	Continuous				
Diabetes Mellitus & Insulin Resistance:					
Reduction in diabetes	Categorical	Maximal weight loss, maximal loss of fat mass, nadir BMI	Continuous	Patient/Visit	Logistic regression, Discrete-time proportional hazards (pooled logistic regression)
Reduction in met. syndrome	Categorical				
Δ in insulin resistance	Continuous				
CVD and Pulmonary Disease:					
Corridor walk time	Continuous	Age, BMI, insulin resistance, blood pressure, liver function, inflammatory markers	Continuous	Patient	Spearman correlation, linear regression
Corridor walk time	Continuous	Gender, diabetes, sleep apnea	Categorical	Patient	ANCOVA
Incident CVD, mortality	Categorical				
Renal Disease:					
Δ in albuminuria	Continuous	Pre/post bariatric surgery	Continuous	Patient	Paired t-tests or analogous non-parametric methods
Δ in GFR	Continuous	Pre/post bariatric surgery	Continuous	Patient	

Table 4.1. (continued). Primary Analytic Methods Used to Evaluate LABS-2 Hypotheses

Outcome Variable	Measurement	Predictor Variable(s)	Measurement	Unit of Analysis	Primary Method(s) Of Analysis
Liver Function:					
Prevalence/severity of non-alcoholic fatty liver disease (NAFLD) (based on histology)	Categorical	Traditional assessment of NAFLD (labs, clinical assessment, visual inspection)	Categorical	Patient	Kappa statistic, predictive value negative
		Race/ethnicity, traditional demographic, clinical, and laboratory assessments	Categorical and continuous	Patient	Binomial and ordinal logistic regression
Short-term post-operative morbidity and mortality	Categorical	Severity of liver disease (biopsy)	Categorical	Patient	Poisson regression
Δ in liver disease (clinical and biochemical)	Continuous	Steatohepatitis (detected on biopsy), weight loss	Categorical	Patient/visit	Linear regression / linear mixed models

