4.2. Sample Size Estimates. As listed in Section 2.1, LABS-2 will evaluate the efficacy of bariatric surgery using a wide range of patient outcomes with various scales of measurement and across many scientific disciplines. Moreover, additional hypotheses regarding the efficacy of bariatric surgery will be developed and evaluated during the course of the study. For these reasons, sample size calculations have been provided for both binary and continuous outcome measures, assuming either single or repeated measurements, and assuming varying proportions of patients within subgroups to be compared. For simplicity, patient and surgical characteristics to be compared are based on two-group comparisons, recognizing that some characteristics may be evaluated using more than two groups and with alternative statistical methods, such as linear tests of trend. Finally, to be conservative, all calculations are based on desired power of at least 90% and two-sided alpha of 0.05.

4.2.1. Comparisons of Proportions Based on Single Outcome Measurement. Table 4.2.2 presents odds ratios detectable at 90% power for comparing binomial proportions of outcome occurrence given various sample sizes, event rates in the reference (control) group, and percentage of all subjects as controls. As seen, with an effective sample size ranging from 1200 to 3200 patients, detectable odds ratios range from 1.32 to 3.10. With the goal of having sufficient statistical power to detect odds ratios of 2.0 or higher, an effective sample size of 2000 patients is sufficient for all conditions with the exception of when a low event rate of 5% is observed in the reference subgroup coupled with a highly imbalanced design in which 90% of all subjects reside within the reference subgroup. Of note, these binomial comparisons of event rates and detectable odds ratios are conservative with respect to the frequent anticipated use of alternative survival analysis methods, when appropriate.

Table 4.2.2. Odds Ratios Detectable at 90% Power Given Various Sample Sizes, Event Rates in Control Subjects (Reference Group) and Proportions of Subject in Reference Group*

Sample Size % of reference group →	5% event rate in reference group			10% event rate in reference group			20% event rate in reference group		
	50%	75%	90%	50%	75%	90%	50%	75%	90%
1200	2.13	2.33	3.10	1.78	1.91	2.44	1.57	1.67	2.05
1400	2.03	2.21	2.90	1.71	1.83	2.30	1.52	1.61	1.95
1600	1.95	2.11	2.74	1.65	1.77	2.19	1.48	1.56	1.88

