4.3. Comparisons of Continuous Outcome Variables Based on Single Outcome

Measurement. Table 4.4 presents effect sizes (difference in mean scores between the 2 groups being compared / common standard deviation) detectable at 90% power given various sample sizes and proportion of all subjects in the control (reference) group. As seen, with an effective sample size ranging from 1200 to 3200 patients, detectable effect sizes range from 0.11 to 0.31. In general, effect sizes less than 0.2 are considered “small” and those from 0.2 to <0.5 are considered “medium” (Cohen 1988). Thus, an effective sample size of 1800 subjects will be sufficiently powered to detect “small” effect sizes under all conditions with the exception of a highly imbalanced design in which 90% of all subjects reside within the reference subgroup.

[figure not shown]
Table 4.4. Effect Sizes for Continuous Outcome Measures Detectable at 90% Power Given Various Sample Sizes and Proportions of Subjects in the Reference Group*

Sample Size	% of All Subjects in Reference Group				
	50%	60%	70%	80%	90%
1200	0.19	0.19	0.20	0.23	0.31
1400	0.17	0.18	0.19	0.22	0.29
1600	0.16	0.17	0.18	0.20	0.27
1800	0.15	0.16	0.17	0.19	0.25
2000	0.15	0.15	0.16	0.18	0.24
2200	0.14	0.14	0.15	0.17	0.23
2400	0.13	0.14	0.14	0.17	0.22
2600	0.13	0.13	0.14	0.16	0.21
2800	0.12	0.13	0.13	0.15	0.20
3000	0.12	0.12	0.13	0.15	0.20
3200	0.11	0.12	0.13	0.14	0.19

*Based on Student’s *t* test and assuming 2-sided alpha of 0.05.

4.4.1. Target Sample Size. Based on the above sample size calculations and the desire to be able to detect odds ratios of at least 2.0 for categorical outcomes and “small” effect sizes for continuous outcomes, a target sample size of 2,400 patients is proposed. This exceeds the estimates of 2,000 patients for discrete outcomes under most circumstances (table 4.2) and 1800 patients for continuous outcomes (table 4.4) so as to conservatively allow for loss to follow-up ranging from approximately 16% to 25%.

5 Study Organization

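### Renal function is hypothesised to remain stable, but the only method listed for the renal outcomes is a paired test of difference, with no margin to say what stable means

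*Protocol*

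**What the plan says.** The Renal Disease paragraph of Section 2.1 makes two predictions of different logical form. Albuminuria is expected to fall. For the second, it is hypothesised that "renal function as reflected by serum creatinine will remain stable after successful bariatric surgery". On measurement it says: "Renal function will be measured by serum creatinine and cystatin and urinary albumin and creatinine (spot urine".

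Section 4.1.2 presents Table 4.1 as setting out the primary methods for the LABS-2 hypotheses. The renal block of that table has two rows, change in albuminuria and change in GFR, each compared before and after surgery at patient level. The one method listed is "Paired t-tests or analogous non-parametric methods". In the text as available it is printed on the albuminuria row and the GFR cell is empty; a cell shared by both rows is the natural reading. Serum creatinine has no row of its own.

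On size, Section 4.2 says that "all calculations are based on desired power of at least 90% and two-sided alpha of 0.05". Section 4.3 says "an effective sample size of 1800 subjects will be sufficiently powered to detect" small effects unless 90% of patients are in the reference group, and sets the scale: "In general, effect sizes less than 0.2 are considered" small. Section 4.4.1 says "a target sample size of 2,400 patients is proposed", which is meant to "allow for loss to follow-up ranging from approximately 16% to 25" percent. No margin, equivalence or non-inferiority method, or confidence-interval criterion for stability appears anywhere in the protocol.

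**The concern.** A paired difference test takes no change as its null hypothesis. That suits albuminuria, where a fall is predicted and rejecting the null supports the prediction. For renal function the prediction is the null itself. Failing to reject can mean that function is stable or that there were too few pairs. Rejecting can mean real deterioration, or a shift too small to matter that a large cohort has measured precisely.

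The point bears on safety. Section 2.1 itself notes that this surgery has been linked to progressive kidney disease, and longer-term safety is part of the primary objective. A statement that renal function was stable would be read as reassurance, and the listed method gives no basis for it. A margin chosen after the data are seen would carry little weight.

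The quantity also needs settling: the hypothesis names serum creatinine, while the table analyses change in GFR.

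**Working it through.** **Inputs.** Two-sided alpha 0.05 and power 90% (Section 4.2); effective N 1,800 (Section 4.3); target N 2,400 (Section 4.4.1); 0.2 SD as the upper limit of a small effect (Section 4.3). Not given: the SD of the pre/post change, a margin, and the number of patients with successful surgery. Results are therefore in SD units of the change; margins, true shifts and subset sizes below are illustrations.

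**The protocol's own figures.** Table 4.4 follows from d = (1.960 + 1.282)/√(N·f·(1−f)), where f is the share in the reference group. With f = 0.5:
- N = 1,800: 3.242/√450 = 0.153 (printed 0.15)
- N = 2,400: 3.242/√600 = 0.132 (printed 0.13)

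Of the 55 cells, 54 agree to two decimals. The other (N = 2,000, 50%) is 0.14496 against a printed 0.15, a rounding matter. Loss: 1 − 2,000/2,400 = 16.7% and 1 − 1,800/2,400 = 25%, in line with Section 4.4.1. These are two-group figures; the protocol gives none for the paired renal test.

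**Paired difference test** (normal approximation).
- Shift detected with 90% power, 3.242/√n: 3.242/42.43 = 0.076 SD at 1,800; 3.242/48.99 = 0.066 SD at 2,400.
- Against the 0.2 SD limit: 0.066/0.2 = 33% and 0.076/0.2 = 38%.
- Smallest observed shift that is significant, 1.960/√n: 0.046 SD at 1,800; 0.040 SD at 2,400.
- Power to declare a change when the true shift is 0.1 SD: 98.9% at 1,800; 99.8% at 2,400.

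The 0.2 benchmark is on the SD of the outcome, not of the change. If the outcome SD is the same before and after surgery and the two values have correlation ρ ≥ 0 (an assumption), the SD of change is √(2(1−ρ)) outcome SDs, at most 1.414. The detectable shift at 1,800 is then at most 0.0764 × 1.414 = 0.108 outcome SD, still well below 0.2.

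**The opposite failure.** With an illustrative 100 pairs and a true shift of 0.2 SD, power is Φ(0.2 × 10 − 1.960) = Φ(0.04) = 0.52. A shift at the protocol's limit would be missed about half the time.

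**Equivalence on the same data** (two one-sided 5% tests, that is, the 90% interval inside ±margin), with a margin of 0.1 SD:
- 1,800 pairs, true change 0: 2Φ(0.1 × 42.43 − 1.645) − 1 = 2Φ(2.598) − 1 = 0.99
- 1,800 pairs, true shift 0.05 SD: Φ(0.05 × 42.43 − 1.645) = Φ(0.476) = 0.68
- 1,800 pairs, true shift 0.0764 SD: Φ(0.0236 × 42.43 − 1.645) = Φ(−0.644) = 0.26
- 600 pairs, true change 0: 2Φ(0.1 × 24.49 − 1.645) − 1 = 0.58

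With a margin of 0.2 SD, 1,800 pairs and a true shift of 0.1 SD: Φ(0.1 × 42.43 − 1.645) = 0.995.

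**One-sided bound on decline.** With a 0.1 SD margin, 1,800 pairs and a true improvement of 0.05 SD: Φ(0.15 × 42.43 − 1.645) = Φ(4.72), above 0.999. Improvement does not count against this version.

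**The case against.** The strongest reply is that Table 4.1 names a family of methods, not a decision rule. A reader might infer that the protocol will call renal function stable whenever p exceeds 0.05 and unstable otherwise; no section says so. A reader might also infer that the paired analysis can never show stability. That holds for the p-value alone: the same paired data give a confidence interval that could show it, once a margin is set. Section 4.1 further allows the final method to be chosen to fit the data, and a margin could sit in an analysis plan that is not at hand.

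Part of this stands. No false conclusion is built into the protocol. But Table 4.1 is presented as the statement of primary methods, the method it gives does not fit this hypothesis, and the general clause names neither an alternative nor a margin.

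The reply is also right that equivalence testing is not free. The 99% power above needs a true change of exactly zero, a margin chosen for illustration and all 1,800 pairs. Section 2.1 expects weight loss to help renal measures, so a two-sided equivalence test could fail because patients improved. The hypothesis also covers only patients with successful surgery, an undefined and possibly much smaller group.

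Creatinine against GFR is the weaker part: GFR may be intended as a quantity derived from creatinine, in which case the wording only needs aligning. A reader might go further and argue that loss of muscle distorts creatinine and that cystatin C should lead. The protocol does not support this: it lists fat-free mass as an outcome without predicting its direction, and ranks neither marker.

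**Conclusion.** The concern holds in a limited form. A prediction of no change is paired with a test whose null is no change, and nothing in the protocol quantifies stable. Non-significance would not show stability. At 1,800 to 2,400 pairs, significance would be reached with 90% power at a mean shift of 0.076 to 0.066 SD of the change, about a third of the protocol's own limit for a small effect.

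This rests on reading the method cell as shared by the albuminuria and GFR rows, on SD units because no SD of change is given, and on most enrolled patients contributing a pair. A smaller successful-surgery subset raises the detectable shift (3.242/√600 = 0.13 SD at 600 pairs) but leaves the logical mismatch untouched. It is one hypothesis among many in an observational cohort and does not affect the target sample size. It is worth correcting because the claim concerns safety and the repair is small.

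**What to change.** Keep the paired test for albuminuria. Give renal function its own entry in Table 4.1 with three elements: a named visit, a margin fixed before analysis, and a reading rule. Stability would be declared only if the 90% confidence interval for mean change lies wholly within the margin. If only decline matters, a one-sided non-inferiority bound is the better choice, since Section 2.1 expects improvement. Define successful surgery for this hypothesis. State whether the outcome is serum creatinine or GFR and, if GFR, from which marker it is derived, and use the same term in Section 2.1 and Table 4.1.

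The cost is one table entry, a matching edit to Section 2.1 and agreement on a margin. No extra patients or samples are needed. The drawback is that power then depends on choices and facts not yet settled: at a 0.1 SD margin it is about 99% with 1,800 pairs and no true change, about 68% if the true shift is 0.05 SD, and about 58% with 600 pairs and no change. The margin should be agreed on clinical grounds, with these figures in view.

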2.2 Secondary Objectives

1. To assess health care utilization of patients undergoing bariatric surgery for treatment of obesity and related co-morbidities.
2. To obtain and store biospecimens (serum, plasma, urine and tissue) for research related to the aims of LABS-2, and for future research into the pathophysiology of obesity and obesity related complications.

Specific hypotheses to be investigated from these secondary objectives are described below:

Health Care Utilization. Patient outcome following bariatric surgery is variable, and hence, so is subsequent use of health services. It is hypothesized that higher levels of BMI pre-surgery will be associated with higher post-surgery health services utilization; hospital readmission rates will be higher for patients who undergo BPD-DS compared to other surgical procedures; and patients who are more physically active following surgery will utilize fewer health services.

Biospecimens. Approximately, 55.5mL of blood and 4.5 of urine will be obtained from LABS-2 participants at pre-specified intervals (see §3.4). Fasting insulin, high sensitive C-reactive protein, lipid profile (HDL, LDL, total cholesterol, triglycerides), HbA1C, serum creatinine, cystatin C, urine creatinine, and urine albumin will be measured at a central laboratory. Aliquots of plasma and serum will be banked for future investigations into parameters such as changes in metabolic parameters and markers of risk. An additional 24mL of whole blood will be drawn to be used for DNA analysis. Additionally, if a liver biopsy is taken during surgery as part of the clinical institution's standard practice, a small portion will be studied by LABS investigators. Non-LABS investigators may access biospecimens through application via the LABS ancillary studies process or a process to be developed by the NIDDK Biospecimens Repository, where the specimens will be stored indefinitely. A spot urine test will be obtained and sent to a central laboratory for creatinine and albumin determinations. Aliquots of urine will be stored at the NIDDK Repository for use in future substudies on nutrition (e.g. – to measure bone markers).

3 Study Design

3.1 Study Summary. The primary goal of LABS-2 is to evaluate the efficacy and safety of bariatric surgery over a longer term than LABS-1, i.e., more than 30 days. Approximately 2,400 patients, will be recruited over 3 years. LABS-2 will include clinical assessments and detailed interviews and questionnaires pre-operatively and at several post-operative time points (30 days, 6 months, 12 months following surgery, and annually thereafter) to assess risks of surgery, and changes in clinical, metabolic, and psychosocial characteristics in patients, and health care utilization following bariatric surgery. Detailed data about the surgical procedure and peri- and post-operative care will also be collected to determine if components of the surgical procedure, and peri-operative and post-operative care as well as clinical/demographic patient characteristics are associated with post-operative risks and changes in patient status. Patients enrolled in LABS-2 will provide blood specimens pre-operatively and post-operatively to address LABS-2 hypotheses and additional samples will be stored at the NIDDK tissue repository for serologic, pathologic and genomic testing of other hypotheses.

3.2 Study Population

3.2.1 Sources of Patients. LABS-2 patients will be selected from people undergoing bariatric surgery at participating sites.

3.2.2 Inclusion Criteria

- Patients at least 18 years of age who undergo bariatric surgery by a LABS-certified surgeon
- Selected by a site-specific sampling algorithm to be approached for inclusion in LABS-2

3.2.3 Exclusion Criteria

- Informed consent not obtained
- Prior bariatric surgery
- Unlikely to comply with follow-up protocol (e.g., travel time from home too long to make visits feasible, unwilling to return for follow-up visits)
- Unable to communicate with local study staff

3.2.4 LABS-certified surgeon

- Performs bariatric surgery at one of the LABS clinical centers
- Has undergone training on the LABS protocol and data collection
- Has successfully completed a certification examination
- Agrees to adhere to LABS protocol and provide required data

3.2.5 Criteria for Study Withdrawal

- Patient withdraws consent
- NIDDK ends the study

3.2.6 Target composition of the database population. LABS-1 (see §1.1) will consist of patients aged 18 years and older undergoing bariatric surgery performed by LABS certified surgeons. Based on current patient demographics and surgeon practices in the participating clinical centers:

- approximately 84% of the patients are expected to be women
- approximately 25% are expected to have a BMI at least 50 kg/m²
- approximately 18% are expected to be African American
- approximately 15% are expected to be Hispanic or Latino
- approximately 25% are expected to have type 2 diabetes
- approximately 2.5% are expected to undergo bariatric surgery with a BPD
- approximately 5% of patients are expected to have a laparoscopic adjustable gastric band placed
- approximately 20% of patients will have an anastomotic sealant used
- approximately 25% of patients will be prescribed low molecular weight heparin
- approximately 25% of patients will be prescribed subcutaneous heparin and
- approximately 25% will have both low molecular weight heparin and subcutaneous heparin
- approximately 22% will be planned open procedures

The goal of LABS-2 is to accrue 2,400 patients. This goal will provide a large enough sample of patients to detect odds ratios of at least 2.0 for categorical outcomes and small effect sizes for continuous outcomes (see § 4.2.4).

3.3 Study Visits and Database Contents. Pre-operative data will be collected (SITE SPECIFIC)...

Patients will be seen 1-30 days prior to surgery for their LABS-2 baseline evaluation. Follow-up data collection will occur at approximately 30 days, 6 months, and 12 months following surgery, and annually. Starting with the 6-year visits, every other year during follow-up, a reduced battery will be collected during a minimal assessment visit in lieu of the standard in-person visit. During the odd years, participants will be asked to come in for the full LABS visit. There will also be data collected about the surgery and at hospital discharge following the bariatric surgery procedure. All data are collected during an in-person visit or via chart review. The tables below indicate the schedule of measures by study visit. A copy of all measures are included in the Appendix (see §10).

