will resolve following bariatric surgery. However, menstrual abnormalities may increase or show no improvement in the first 12 months following surgery when weight loss is often rapid (Schuetz 2004).

Risks of Bariatric Surgery. Bariatric surgeries impart potential long-term risks that are not necessarily faced by those who do not undergo such procedures or that differ depending on aspects of the surgical procedure (Deveney 2004). Thus, potential adverse outcomes such as death, outlet obstruction, wound complications, and surgical revisions and re-operations will be tracked. Pre-operative characteristics including demographics (e.g., sex, race), BMI, and co-morbidities will be examined for their relationships with these outcomes (Perugini 2003, Liu 2003, Livingston 2002). Additionally, the occurrence of stomal ulcer, PE/DVT, and dehydration will be examined in relationship to limb length, pouch size, and types of anastomoses used in the gastric bypass procedure. Hypotheses related to surgical risk are that males will have higher mortality than females, wound infections are more common among patients who undergo an open or laparoscopic converted to open bariatric surgery than among patients undergoing a laparoscopic procedure, that nutritional complications, including re-admission to hospital, will be more common in patients undergoing more malabsorptive operations than among those undergoing a more restrictive operation, that total morbidity is higher in males than females and is positively associated with pre-operative BMI, that African-Americans will have lower percent excess weight loss results following bariatric surgery than patients in other racial groups, and that patients who undergo bariatric surgery without any pre-operative thromboembolism prophylaxis will experience a higher deep vein thrombosis or pulmonary embolism rate than patients who do receive pre-operative prophylaxis.

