1800	1.88	2.03	2.61	1.61	1.71	2.11	1.45	1.53	1.81
2000	1.83	1.97	2.50	1.57	1.67	2.04	1.42	1.49	1.76
2200	1.78	1.91	2.41	1.54	1.63	1.98	1.40	1.47	1.72
2400	1.74	1.86	2.34	1.52	1.60	1.93	1.38	1.44	1.68
2600	1.71	1.82	2.27	1.49	1.58	1.88	1.36	1.42	1.65
2800	1.67	1.79	2.21	1.47	1.55	1.84	1.35	1.41	1.62
3000	1.65	1.76	2.16	1.45	1.53	1.81	1.33	1.39	1.60
3200	1.62	1.73	2.12	1.44	1.51	1.78	1.32	1.38	1.57

*Based on chi-square test with continuity correct and assuming 2-sided alpha of 0.05.

4.2.3. Comparisons of Proportions Based on Repeated Outcome Measurements. Table 4.2.4 presents odds ratios detectable at 90% power for comparing binomial proportions of repeated outcome measurements given various sample sizes, event rates in the reference group, and correlations between repeated measurements. These estimates illustrate the increase in variance that occurs (and hence required sample size) with correlated observations over time. The impact of this within-person correlation on the odds ratio that is detectable for a given sample size is illustrated in the formula below, as described by Diggle (2002).

$$m = \frac{\{z_{\alpha}(2p^*q^*)^{1/2} + z_Q(p_Aq_A + p_Bq_B)^{1/2}\}^2 (1+(n-1)\rho)}{nd^2}$$

- where m = number of subjects needed per group
 α = type I error rate
 p = binomial proportion in each group (A, B), $p^* = (p_A + p_B) / 2$
 $q = 1 - p$, $q^* = 1 - p^*$
 Q = 1 - desired power (proportion)
 n = number of repeated observations per person
 ρ = correlation among repeated observations
 d = smallest meaningful difference to be detected between groups A and B

All of the above estimates assume equal distribution of patients in the two groups being compared and four repeated outcome measurements. As seen, with an effective sample size ranging from 1200 to 3200 patients, detectable odds ratios range from 1.22 to 1.99. By way of comparison with single outcome measurements and equal distribution of patients in the two groups being compared (previous table 4.2), corresponding detectable odds ratios range from 1.32 to 2.13, indicating the gain in power achieved by use of repeated measurements.

Table 4.2.4. Odds Ratios Detectable at 90% Power Given Various Sample Sizes, Event Rates in Control Subjects (Reference Group), and Correlations Between Repeated Measurements*

Sample Size Correlation→	5% event rate in reference group			10% event rate in reference group			20% event rate in reference group		
	0.2	0.4	0.6	0.2	0.4	0.6	0.2	0.4	0.6

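### Section 3.2.6 claims without qualification that 2,400 patients detect odds ratios of 2.0 and small effects, but the protocol's own tables and its expected BPD share contradict this

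*Protocol*

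**What the plan says.** **Target and claim (3.2.6).** "The goal of LABS-2 is to accrue 2,400 patients". The next sentence concludes: "This goal will provide a large enough sample of patients to detect odds ratios of at least 2.0 for categorical outcomes". It adds small effects for continuous outcomes and refers the reader to 4.2.4. Table 4.2.4 assumes two equal groups and four measurements per patient.

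**Expected mix (3.2.6).** The list just above that claim includes "approximately 2.5% are expected to undergo bariatric surgery with a BPD". The list is introduced as describing LABS-1.

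**Hypotheses on small groups or rare events.** Section 2.2 predicts that "hospital readmission rates will be higher for patients who undergo BPD-DS compared to other surgical procedures". Section 2.1 (Nutrient Deficiencies) predicts more fat-soluble vitamin deficiency after duodenal switch. Section 2.1 (Risks of Bariatric Surgery) predicts that "males will have higher mortality than females". No event rates are given for any of these.

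**Power basis.** Section 4.2 states that "all calculations are based on desired power of at least 90% and two-sided alpha of 0.05". The footnote to Table 4.2.2 reads "Based on chi-square test with continuity correct and assuming 2-sided alpha of 0.05". Tables 4.2.2 and 4.4 stop at a 90% reference share, and Table 4.2.2 stops at a 5% event rate.

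**Caveats.** Section 4.2.1 says 2,000 patients are enough for an OR of 2.0 with one exception: a 5% rate together with "a highly imbalanced design in which 90% of all subjects reside within the reference subgroup". Section 4.3 makes a similar exception for continuous outcomes. Section 4.4.1 says 2,000 suffices for discrete outcomes in most circumstances and allows for losses of roughly 16% to 25%.

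**The concern.** The sentence in 3.2.6 is the protocol's summary justification for its size, and it drops every condition that section 4 attaches. Its cross-reference leads to a table that cannot show the effect of imbalance. The procedure mix printed directly above it includes a group far smaller than the most extreme split in any table, and that group carries named hypotheses.

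A reader who relies on 3.2.6 would take a non-significant BPD-DS or mortality-by-sex result as meaningful evidence against a doubling of the odds. For those comparisons the study may be more likely to miss such an effect than to find it. The caveats that do exist are also incomplete against the protocol's own table.

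**Working it through.** **Inputs.** Two-sided alpha 0.05 and 90% power (4.2). Continuity-corrected chi-square (Table 4.2.2 footnote). N = 2,400 (3.2.6). N = 2,000 and 1,800 (4.4.1), the latter being 2,400 × 0.75. BPD 2.5% and women 84% (3.2.6). Female-to-male ratio about 4:1, or 80:20 (8.4). Mortality of 0.5% to 2% is my assumption.

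**Formulas.** Let p0 be the reference rate, p1 = OR·p0/(1 − p0 + OR·p0), d = p1 − p0, k = n1/n0, and p̄ the pooled rate with q̄ = 1 − p̄.
- n0 = [1.960·√((1 + 1/k)·p̄q̄) + 1.282·√(p0q0 + p1q1/k)]² / d²
- With continuity correction: n0′ = (n0/4)·[1 + √(1 + 2(k + 1)/(k·n0·d))]², and N = n0′(1 + k). Solve for OR at fixed N.
- Continuous outcome: effect = 3.242/√(N·r(1 − r)), where r is the reference share.

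**Step 1: reproduce the plan.** The rows for N = 1,800, 2,000 and 2,400 of Table 4.2.2 come out within 0.01. At N = 2,400 and 90:10 the ORs are 2.34, 1.93 and 1.68, as printed. For Table 4.4, 3.242/√(2,400 × 0.9 × 0.1) = 3.242/14.70 = 0.22, as printed.

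**Step 2: read the printed table against the target of 2.0.**

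| N analysed | Cells of Table 4.2.2 above 2.0 |
|---|---|
| 2,400 | 5% rate, 90:10: 2.34 |
| 2,000 | 5%, 90:10: 2.50; 10%, 90:10: 2.04 |
| 1,800 | 5%, 90:10: 2.61; 10%, 90:10: 2.11; 5%, 75:25: 2.03 |

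So the single exception in 4.2.1 is incomplete at its own N of 2,000. For discrete outcomes the margin in 4.4.1 is (2,400 − 2,000)/2,400 = 16.7%. The 25% figure belongs to the 1,800 used for continuous outcomes.

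**Step 3: BPD share of 2.5%.** 0.025 × 2,400 = 60 against 2,340.

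| N | OR at 5% | OR at 10% | OR at 20% | Effect (SD) |
|---|---|---|---|---|
| 2,400 | 4.17 | 3.16 | 2.60 | 3.242/√58.5 = 0.42 |
| 1,800 | 4.92 | 3.66 | 2.97 | 3.242/√43.875 = 0.49 |

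Hand check at a 10% rate and N = 2,400: OR 3.16 gives p1 = 0.316/1.216 = 0.260, so d = 0.160. The required difference is 1.960 × 0.0399 + 1.282 × 0.0570 + ½(1/60 + 1/2,340) = 0.078 + 0.073 + 0.009 = 0.160.

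At 30% and 50% rates with N = 2,400 the ORs are 2.43 and 2.48, so no rate tried brings the figure to 2.0. Power for OR 2.0 at 5%, 10% and 20% is 30%, 47% and 64%; without the continuity correction it is about 39%, 53% and 69%.

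**Step 4: repeated measurements.** The factor in 4.2.3 for four measurements is (1 + 3ρ)/4, which is 0.40 at ρ = 0.2 and 0.55 at ρ = 0.4. Without continuity correction, OR 2.0 at 97.5:2.5 needs 4,464 patients at a 20% rate and 7,216 at a 10% rate on a single measurement.
- 20% rate: 4,464 × 0.40 ≈ 1,790 at ρ = 0.2; 4,464 × 0.55 ≈ 2,455 at ρ = 0.4.
- 10% rate: 7,216 × 0.40 ≈ 2,890 at ρ = 0.2.

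I used the formula of 4.2.3 at 90% power. It gives smaller detectable ORs than Table 4.2.4 prints (1.43 against 1.48 at N = 2,400, 5% rate, ρ = 0.2), so this step favours the protocol.

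**Step 5: mortality by sex, N = 2,400.**

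| Split | 5% | 2% | 1% | 0.5% |
|---|---|---|---|---|
| 80:20 | 1.95 | 2.62 | 3.54 | 5.13 |
| 84:16 | 2.05 | 2.80 | 3.83 | 5.63 |

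**The case against.** The best defence has four parts.

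- **Caveats exist.** Sections 4.2.1, 4.3 and 4.4.1 each limit the claim, and section 4.2 explains that two-group grids were used for simplicity. This stands for those sections, so they cannot be called unqualified. It does not rescue 3.2.6, which repeats none of the limits, and the caveat in 4.2.1 is itself incomplete.
- **The mix is that of LABS-1.** LABS-2 is a subset chosen by a site-specific sampling algorithm (3.2.2). This stands as a condition: about 60 BPD patients is a projection, not a stated number. But no oversampling of BPD is described, and the list directly precedes the LABS-2 claim.
- **The planned methods are stronger than a single chi-square.** Table 4.1 plans Cox, Poisson and GEE models, and 4.2.1 calls the binomial figures conservative. This stands in part: at a 20% rate and ρ = 0.2 the BPD comparison reaches OR 2.0. It does not at a 10% rate, and death is not a repeated outcome.
- **Nothing says a null result would be read as excluding OR 2.0.** True. The misreading is a risk, not a stated intention.

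A reader might also infer wider failures that the documents do not support. A sex difference in diabetes improvement is not hypothesised: 2.1 (Gender Issues) says insulin resistance will matter more than gender, and Table 4.1 allows visit-level analysis. No band-specific hypothesis is set in 2.1 or 2.2, and at the 5% band share the detectable OR depends on the event rate (3.01, 2.38, 2.01 and 1.90 at 5%, 10%, 20% and 30%, N = 2,400). Comparisons by sex do not fail in general, since at 80:20 and a 5% rate the OR is 1.95.

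**Conclusion.** The point holds for the unqualified claim in 3.2.6 and for the incomplete limits in 4.2.1 and 4.4.1. Two parts need no assumption beyond the protocol's tables: the targets are missed at 90:10 with N = 2,400 (OR 2.34 at a 5% rate; 0.22 SD), and further cells exceed 2.0 at N = 2,000 (2.04) and N = 1,800 (2.11 and 2.03).

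The BPD part rests on LABS-2 having roughly the LABS-1 share. Given that, the single-measurement detectable OR is 2.60 to 4.17 for rates of 20% down to 5%, and the detectable effect of 0.42 SD is medium on the scale in 4.3. The mortality part rests on assumed rates: OR 2.6 to 5.6 for 2% down to 0.5%, with the target roughly met at 5%.

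It would be tempting to conclude that the tables are miscalculated or that 2,400 is too few. Neither follows: Tables 4.2.2 and 4.4 reproduce, and for most conditions within the grid the target is met.

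**What to change.** 1. In 3.2.6, limit the claim to the splits and event rates that Tables 4.2.2 and 4.4 support, carry over the imbalance exceptions, and refer to those tables and 4.4.1 rather than to 4.2.4 alone.
2. In 4.2.1, add the 10% rate with a 90:10 split as a second exception at N = 2,000.
3. In 4.4.1, say that the margin for discrete outcomes is about 17%, and that at 25% loss the 5% rate with 75:25 and the 10% rate with 90:10 also exceed 2.0.
4. Add a short table of detectable OR and effect size at the expected LABS-2 BPD share, before and after 25% loss, and of detectable OR for mortality by sex at low event rates. If the sampling algorithm raises the BPD share, state the share and use it. If band figures are shown, give them by event rate.
5. Report the BPD/BPD-DS and mortality-by-sex comparisons as estimates with 95% confidence intervals, so that non-significance is not taken as absence of a two-fold effect.

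The cost is some rewording, one table, and less favourable stated figures. Sample size and data collection are unchanged.
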